increase SZ risk, ocular examination identified bilateral retinal vascular tortuosity¹⁰. In a cross-sectional study, Appaji et al, (2019) demonstrated that patients with SZ had significantly increased retinal venules¹¹, tortuosity¹², capillary network¹³, and vessel trajectory¹⁴ compared to controls, with retinal vessel diameter being associated with cognitive deficits in SZ¹⁵. While these findings have laid the foundation for understanding retinal pathology in SZ, there are several limitations associated with fundus imaging, including reduced image resolution and absence of retinal depth determination. Advances in retinal imaging, such as swept-source optical coherence tomography angiography (SS-OCTA), provide greater microvascular clarity to visualize the retina non-invasively, in a more detailed, quicker, and cost-effective manner. In a pilot study using SS-OCTA, we identified greater vessel length (SD), density (VD), capillary network (FD), and diameter (VDI) in the superficial layer of patients with chronic psychosis compared to HC⁵.

The pathophysiological mechanisms underlying these retinal microvascular changes are not entirely understood, but they have been associated with inflammation (including CRP), endothelial dysfunction, reactive oxygen species and hypoxia/ischemia, which have also been consistently observed in SZ. While it is currently unclear whether venular diameter plays a causal role in the development of SZ, it has been hypothesized that smaller retinal arterioles and wider venules may reflect cumulative structural damage to the microvasculature from inflammation/endothelial dysfunction and indicate problems with the oxygen supply to the brain.

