- All side effects and vital parameters will be recorded during the infusion and 2 hours following the infusion by CRC nursing.
- Any abnormal, clinically significant vital signs will be recorded as adverse events.

Discharge Procedure

- Gross motor and cognitive function, ataxia, reflexes/clonus will be evaluated and documented by a study PI ([name]) prior to discharge.
- Before being discharged patients should be awake and alert, feeling well, with no nausea, vertigo, or dizziness.
- There should be no significant change in vital signs from prior to infusion.
- They will be given a small meal before discharge from the CRC.
- Patients will be instructed not to drive. If necessary, the study nurse will release them to the
 care of an adult family member or caregiver, who will accompany the patient home. If
 needed, a trained Research Assistant will contact the participants support system to ensure
 transportation is coordinated.

Study Drug Handling

- Nitroprusside will be compounded by research pharmacy in 5% dextrose
- 5% dextrose will be used as placebo
- Study drug will be stored at room temperature and the required amount will be released from the pharmacy to the CRC at the time a patient is scheduled for the protocol.
- Study drug will be provided in light-blocked bags with labeling to ensure blinding of study staff.

Nitroprusside standard concentration is 50mg/250mL of D5W and the concentrated version is 100mg/250mL.

Institutional Approvals

Critical Care Executive – [name] and [name] – Approval granted on 9/8/21 Critical Care Practice – [name] and [name] – Approval granted on 9/8/21

B. Statistical Considerations

Power calculation: With 16 ECS individuals in the SNP group and 16 in the placebo group we will have >80% power to detect a 10-point PANSS difference between the placebo and treatment groups, with a SD of 6, alpha of 0.05, 2-sided alternative hypothesis, 2-sample t-test, based on the sample size suggested by the retinal vessel differences in our pilot data. The above-mentioned sample size was determined based on our pilot SS-OCTA data, which suggests that we will have >70% power to detect group differences of at least 0.007 (estimated standard deviations of skeletal density =0.008, significance level=0.05, two-sided t-tests).

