Baseline demographic details will be compared between the SNP and placebo groups using independent-samples t tests or Mann-Whitney U tests where appropriate using R software. Categorical data will be compared using chi-square tests. Effect sizes will be provided using Cohen's d. The primary outcome (PANSS) will be analyzed using a 2 (treatment group) × 5 (time point) mixed analysis of variance (ANOVA). Analyses of secondary outcome measures will be compared using a 2-group x 4 time point mixed ANOVA for cognition and a 2 x 2 for retinal measures. The relationship between baseline or change in retinal vessel measures or CRP and change in PANSS scores or cognition will be performed using Pearson's (parametric) or Spearman's (non-parametric) correlation.

C. Subject Selection

Population: Men and women, 18-60 years of age, from diverse background, symptomatic, with early course schizophrenia, and meet all study inclusion and exclusion criteria.

Inclusion criteria for ECS patients are: a DSM-V diagnosis of SZ or schizoaffective disorder with ≤5 years from the onset of psychosis and up to 2 years of lifetime exposure to antipsychotics, total score of ≥55 on the PANSS with a score of ≥3 on 1 or more PANSS Positive Scale items (delusions, conceptual disorganization, hallucinatory behavior, suspiciousness, or unusual thought content) and/or score of ≥3 on the CGI-S scale, taking antipsychotic for 8 weeks with a stable dose of 4 weeks (no medication change will be allowed during the trial), English proficiency, understands and is able, competent and willing to give informed consent in accordance with the International Conference on Harmonization Good Clinical Practice Guidelines.

Exclusion criteria are:

- Presence of renal, hepatic, cardiac, hematologic, neurologic impairments or abnormal physical exam.
- Presence of retinal disease (myopia >4.0 diopters)

- Baseline systolic BP <100mmHg or symptomatic orthostatic hypotension (systolic BP <90 mmHg or diastolic BP <60 mmHg) with any of the following: lightheaded or dizzy, blurry vision, weakness, syncope, confusion, nausea.
- Pregnant or breastfeeding (pregnancy test at screening visit and prior to randomization).
- Abnormal laboratory testing (see appendix)
- Treatment with medications that may interfere with the metabolism or excretion of SNP or are associated with drug-drug interactions (see list of medications below).
- Prior history of intolerance to SNP
- Currently taking clozapine or chlorpromazine

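### The retinal power statement of more than 70% does not follow from its own printed inputs: the named two-sided t-test gives about 67%

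*Combined protocol and SAP*

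**What the plan says.** Section B3.B, Power calculation, makes two power statements for one sample size, introduced by "With 16 ECS individuals in the SNP group and 16 in the placebo group". The first concerns the PANSS: 10 points, standard deviation 6, power above 80%. The second concerns retinal skeletal density: "we will have >70% power to detect group differences of at least 0.007 (estimated standard deviations of skeletal density =0.008", with "significance level=0.05, two-sided t-tests".

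The paragraph says twice that the retinal data are the source of the sample size: "based on the sample size suggested by the retinal vessel differences in our pilot data", and again "The above-mentioned sample size was determined based on our pilot SS-OCTA data". It prints no unrounded pilot values and names no formula or software.

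The analysis text that follows in B3.B plans a "mixed ANOVA for cognition and a 2 x 2 for retinal measures", and the Outcome paragraph in B3.A lists the retinal measurements at 0 and 5 hours.

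**The concern.** A power statement is conditional on its stated inputs, and here every input is on the page: sample size, difference, standard deviation, alpha, sidedness and test. A reader should be able to put them together and obtain more than 70%. The reader instead gets a figure below 70%.

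The stake is modest. Retinal measures are a secondary outcome of a pilot trial. But this calculation is the only stated source of 16 per arm, so it should be reproducible.

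**Working it through.** **Inputs**, all from the Power calculation paragraph in B3.B:

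- n = 16 per arm (32 in total, which agrees with section B6, Recruitment)
- difference = 0.007
- standard deviation = 0.008
- alpha = 0.05, two-sided
- two-sample t-test
- stated power: above 70%

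**Standardised difference.** d = 0.007 / 0.008 = 0.875.

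**Noncentrality.** d × √(n/2) = 0.875 × √8 = 2.475.

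**Closest reproduction of the plan's figure: normal approximation.** Power = Φ(2.475 − 1.960) = Φ(0.515) = 0.697, or 69.7%. This rounds to 70% but is not above it. It is a plausible origin of the figure, though the plan does not say so.

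**The test the plan names.** With 30 degrees of freedom the two-sided critical value is 2.042. The noncentral t distribution with noncentrality 2.475 gives power 0.668, or 66.8%. A simulation of 200,000 trials gives the same value (0.668). A one-sided t-test would give 78.0%, but the plan specifies two-sided tests.

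**What 70% would require with 16 per arm.**

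| Method | d needed | Difference at standard deviation 0.008 | Standard deviation at difference 0.007 |
|---|---|---|---|
| t-test | 0.908 | 0.00726 | 0.00771 |
| Normal approximation | 0.878 | 0.00703 | 0.00797 |

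**Power by number analysable per arm** (t-test, printed inputs):

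| n per arm | Power |
|---|---|
| 15 | 63.8% |
| 16 | 66.8% |
| 17 | 69.6% |
| 18 | 72.3% |

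**Effect of rounding.** Assume both inputs were rounded to three decimals, so the difference lies in 0.0065–0.0075 and the standard deviation in 0.0075–0.0085. At the unfavourable corner (0.0065 and 0.0085) the t-test power is 55.3%. At the favourable corner (0.0075 and 0.0075) it is 78.1%. The range covers 70%.

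**The PANSS statement, for comparison.** d = 10/6 = 1.667; noncentrality = 1.667 × √8 = 4.714; t-test power 99.5%. The stated power above 80% holds.

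**The case against.** The strongest reply is rounding. Both inputs have one significant figure, and a pilot standard deviation of 0.0077, which prints as 0.008, would already give 70.1% by the t-test. By the normal approximation the shortfall is only 0.3 points, well inside rounding. If the true values were spread evenly over the rounding range (an assumption), about a quarter of the pairs would exceed 70% by the t-test and nearly half by the normal approximation. The sponsor's own calculation may therefore have been correct. That stands: the documents can neither confirm nor refute it. It does not rescue the sentence as printed, because the statement is made for 0.007 and 0.008, and rounding could equally have flattered the result.

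A second reply is that 67% is not the power of the planned retinal analysis either. The 2 × 2 analysis tests the change from 0 to 5 hours. If 0.008 is a standard deviation at one time point, the standard deviation of change is 0.008 × √(2(1 − ρ)), where ρ is the correlation between the two times. The plan gives no ρ. Assumed values of 0.4, 0.5, 0.6 and 0.7 give t-test power of 59%, 67%, 76% and 87%. This is fair, and it is why any restated figure should say what it refers to. It does not make the printed sentence correct, since that sentence claims its result for a t-test with standard deviation 0.008.

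A third reply is that nothing depends on three points of power. Neither the design nor the primary analysis would change. That supports a minor rating, not leaving the sentence as it is.

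**Conclusion.** The concern holds, as a minor one. On the printed inputs the two-sided t-test gives 66.8% and the normal approximation 69.7%; no two-sided calculation on those values exceeds 70%. The shortfall is 3.2 points by the named test.

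The result takes the printed inputs at face value and assumes all 16 per arm are analysable for the retinal measure. Any loss lowers the figure, and the plan makes no allowance for it, although the SS-OCTA paragraph in B3.A excludes poor-quality images. The finding is limited to the mismatch between the printed inputs, the named test and the printed power. It does not show that the original calculation was wrong, and it leaves the PANSS power statement untouched.

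**What to change.** Reword the retinal sentence in B3.B in one of these ways:

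- State power of about 67% for a difference of 0.007 at standard deviation 0.008, with 16 analysable patients per arm and a two-sided two-sample t-test.
- Give about 0.0073 as the difference detectable with 70% power at standard deviation 0.008.
- Keep the claim of more than 70%, but only if the unrounded pilot difference and standard deviation and the method are printed and support it. If those values are to hand, this is the most informative choice.

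While editing, it would help to add one sentence saying whether 0.008 is a single-time standard deviation. It appears to be: the SS-OCTA pilot described in B2 reports results "in the superficial layer of patients with chronic psychosis compared to HC", with no repeat imaging mentioned, whereas the planned analysis concerns the 0 to 5 hour change. This is a clarification, not a second error.

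The cost is one or two sentences. Enrolment, design and the primary analysis stay as they are.

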NCT Number: NCT04986072

Official Title: Sodium Nitroprusside in Early Course Schizophrenia

Document Type: Study Protocol and SAP

Document Date: 07/17/2023

PART B STUDY DESCRIPTION

Title of Protocol	Proof of Mechanism Study using a Retinal Biomarker to Predict Treatment Response with Intravenous Sodium Nitroprusside in Symptomatic Early Course Schizophrenia
Principal Investigator	[name]

B1. PURPOSE OF PROTOCOL

- 1. The main purpose of this proposal is to determine the effectiveness of a single intravenous administration of sodium nitroprusside (SNP) (0.5 mcg/kg/min for 4 hours) on positive and negative symptoms in symptomatic Early Course Schizophrenia (ECS).
- 2. To examine the effect of SNP on cognition and retinal imaging phenotypes in ECS, and whether baseline retinal microvasculature or inflammation (CRP levels) correlate with a change in psychosis symptoms or cognition.

We hypothesize that SNP will improve psychosis symptoms and cognition in symptomatic ECS and that this change can be predicted by retinal vessel morphology or CRP levels. We predict that SNP will improve oxygen supply and reduce inflammation, which will be evidenced by reductions in retinal vessel phenotypes.

B2. SIGNIFICANCE AND BACKGROUND FOR THE STUDY

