Nitric oxide (NO) signaling is a potential mechanism for protecting the microvasculature against oxidative stress, inflammation and endothelial dysfunction¹⁶. NO-donors (NOD) can protect nerve tissue from injury and preserve the integrity of the blood brain barrier, suggesting that cerebral vascular endothelium is essential in the control of vascular inflammatory and oxidative responses, leukocyte migration, and the production of inflammatory mediators¹. In addition to reducing oxidative stress and inflammation, NOD can increase cerebral and retinal blood flow¹⁶. In healthy volunteers, SNP dose dependently increases retinal arteriolar/venular diameter, and leukocyte flow¹⁷. However, in pathologic states such as ischemia, SNP can enhance neuroprotection by increasing arteriolar diameter and reducing venular leukocyte adhesion (i.e., reduced venular diameter), which together facilitate blood flow¹⁶. Preclinical and clinical evidence have shown that SNP may have an antipsychotic profile. In preclinical studies, SNP has been used to prevent SZrelated behaviors in a spontaneously hypertensive rat model¹⁸. Five clinical studies to date have examined the effects of SNP on psychosis symptom improvement with mixed results. In one study, a single infusion of SNP resulted in an immediate improvement in overall psychosis and negative symptoms in an antipsychotic medicated ECS group with <5 years illness duration, an effect that persisted for 4 weeks¹⁹. However, four studies performed in chronic SZ did not find any evidence of symptomatic improvements, with two of these studies providing repeated infusions of SNP^{20–23}. There were several limitations with these negative studies: older patient population, longer durations of illness (8-17 years), and the absence of a treatment biomarkers. These studies neglected to consider an alternative mechanism of action for SNP, which would include the protection against inflammatory mediated microvascular dysfunction. Another important factor to consider is that while ~70 randomized control trials to date have examined adjunctive antiinflammatory drugs on psychosis symptoms or cognition in SZ²⁴, six of these have performed post hoc analyses of participants with elevated levels of individual inflammatory markers (such as CRP), and their findings strongly suggest that ECS individuals with elevated peripheral inflammation have the greatest benefit with anti-inflammatory drugs²⁴. Thus, it is conceivable that treatment effects could be stronger in participants with elevated markers of inflammation or disruptions in related pathways. As a result, in order to SNP to be effective it should be administered to patients with ECS. Thus, further work is needed to determine whether the effect of SNP treatment is dependent on a patient's illness duration and whether a retinal biomarker for microvascular dysfunction/inflammation can predict treatment response to SNP. There is a growing literature on how increased peripheral inflammation and

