SS-OCTA: Images will be obtained using the Zeiss PLEX Elite 9000, which is a quick, inexpensive, and non-invasive method for acquiring retinal images with an axial resolution of ~5µm and a scan depth of 3.0mm. Automated layer segmentation provides four horizontal depth-resolved retinal slabs: superficial (SRL), deep (DRL), outer retinal layer (ORL) and the choriocapillaris. Participant images will be excluded for low signal strength (≤6), blink artifacts, doubling artifacts, media opacity obscuring visualization of the vasculature, and/or segmentation errors. Manual segmentation editing will be conducted to ensure proper layer assessment. Microvessels for the SRL, DRL, and choriocapillaris slab will be processed using a custom semiautomated algorithm we developed to rapidly quantify several vessel parameters including vessel density, length, diameter, and capillary network. All images will be independently analyzed and compared among study subjects by two graders blinded to the group assignment.

Outcome: Primary outcomes include the change in PANSS positive and negative scores (2hrs, 5hrs, 1wk, 2wk, and 4wks) in the SNP group compared to placebo. The secondary outcomes include the change in overall cognition (0hr, 1wk, 2wk, and 4wks) and retinal microvascular measures (0hr, 5hrs), as well as examining the relationship between baseline or change in retinal vessel measures or CRP and the change in psychosis symptoms and cognition after SNP treatment compared to placebo.

SNP Treatment Protocol

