-Risk C: Monitor therapy

Alfuzosin

Amphetamines

Clozapine and Chlorpromazine

Barbiturates

Benperidol

Blood Pressure Lowering Agents

Brigatinib

Brimonidine (Topical)

Dapsone (Topical)

Dexmethylphenidate

Diazoxide

DULoxetine

Herbs (Hypertensive Properties)

Herbs (Hypotensive Properties)

Local Anesthetics

Lormetazepam

Methylphenidate

Molsidomine

Naftopidil

Nicergoline

Nicorandil

Nitric Oxide

Pentoxifylline

Pholcodine

Prilocaine

Prostacyclin Analogues

Quinagolide

Sodium Nitrite

Sildenafil or Tadalafil

Yohimbine

References

- 1. Brown, H. E. *et al.* Efficacy and Tolerability of Adjunctive Intravenous Sodium Nitroprusside Treatment for Outpatients With Schizophrenia: A Randomized Clinical Trial. *JAMA Psychiatry* **76**, 691 (2019).
- Hallak, J. E. C. et al. Rapid Improvement of Acute Schizophrenia Symptoms After Intravenous Sodium Nitroprusside: A Randomized, Double-blind, Placebo Controlled Trial. JAMA Psychiatry 70, 668 (2013).
- 3. Stone J.M. et al. The effect of sodium nitroprusside on psychotic symptoms and spatial working memory in patients with schizophrenia: a randomized, double-blind, placebo-controlled trial. *Psychological Medicine* 46, 3443-3450 (2016).
- 4. Wang X. et al. Sodium nitroprusside treatment for psychotic symptoms and cognitive T deficits of schizophrenia: A randomized, double-blind, placebo-controlled trial. *Psychiatry Research* 269, 271-277 (2018).
- 5. Adelino et al. Treatment-resistant schizophrenia A RCT on the effectiveness of repeated-dose sodium nitroprusside. Schizophr Res. 2021 May;231:70-72.

B4. POSSIBLE BENEFITS

There are no direct benefits to subjects. However, as shown by previous clinical studies, an immediate improvement in overall psychosis and negative symptoms in participants with ESZ may be achieved with SNP treatment.

Potential benefits to society include increased understanding of the pathophysiology of schizophrenia and the personalization of treatment early in the course of schizophrenia illness. We are expecting to have an impact on the growing consensus in immunopsychiatry and neuro-ophthalmology that the retina provides a window into the brain that informs our understanding of brain pathophysiology and identifies biomarkers of treatment response with this study.

B5. POSSIBLE RISKS AND ANALYSIS OF RISK/BENEFIT RATIO

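### The PANSS ANOVA has no baseline covariate and no named treatment test; adjusting for pre-infusion PANSS would add power at moderate effects at almost no cost

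*Combined protocol and SAP*

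**What the plan says.** The primary analysis is one sentence in B3.B, Statistical Considerations: "The primary outcome (PANSS) will be analyzed using a 2 (treatment group) × 5 (time point) mixed analysis of variance (ANOVA"). It names no deciding effect (group, group-by-time or a visit contrast), does not say whether raw or change scores enter, and lists no covariate.

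The Outcome paragraph of B3.A gives the endpoint and its times: "Primary outcomes include the change in PANSS positive and negative scores (2hrs, 5hrs, 1wk, 2wk, and 4wks"). There are five times and none is 0hr. The next sentence does list 0hr: "The secondary outcomes include the change in overall cognition (0hr, 1wk, 2wk, and 4wks) and retinal microvascular measures (0hr, 5hrs"). Those counts, four and two, match the secondary models; for example, "Analyses of secondary outcome measures will be compared using a 2-group x 4 time point mixed ANOVA for cognition". The five PANSS levels are therefore most naturally all post-baseline. This is an inference: the design figure is not shown, and the Schedule of Events that B3.A mentions is not in the text supplied.

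On the timing of benefit, B4 expects that "an immediate improvement in overall psychosis and negative symptoms in participants with ESZ may be achieved with SNP treatment", and B2 cites one early-course study with "an effect that persisted for 4 weeks". B2 also reports that "four studies performed in chronic SZ did not find any evidence of symptomatic improvements".

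**The concern.** There are two matters, the first being the main one.

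**Baseline.** If the endpoint definition is followed, each participant's pre-infusion score is subtracted. Subtraction fixes the weight on baseline at one. Adjustment estimates the weight and is more precise in every scenario run here. The trial has 16 per arm, and four of the five earlier studies that B2 cites (all four in chronic illness) found no improvement, so effects well below 10 points are plausible. At such effects the lost precision matters.

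**Which effect is the test.** A mixed ANOVA yields a group effect and a group-by-time effect. When 0hr is a level, group-by-time is the natural treatment test. When all levels are post-baseline, it asks only whether the arm difference changes between 2 h and 4 weeks; the group effect asks whether there is a difference. The two can disagree, and leaving the choice until the data are seen inflates the false-positive rate.

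**Working it through.** **Inputs from the documents (B3.B, B3.A).** 16 per arm; 10-point difference; SD 6; two-sided alpha 0.05; two-sample t-test; five PANSS times.

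**Assumptions not in the documents.** SD 6 applies to each rating (the plan does not say which score it belongs to). Baseline-to-post correlation rb is 0.5/0.6/0.7, and post-to-post correlation rw is 0.6/0.7/0.8, equal for all pairs. Data are complete. Simulated figures come from 40,000 runs per cell.

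**1. The plan's own figure.** Noncentrality = (10/6) × √(16/2) = 1.667 × 2.828 = 4.71. With 30 df, power is 99.5% (normal approximation 99.7%). The stated figure of more than 80% is true with a wide margin.

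**2. Variance of the averaged arm difference**, in units of SD² and per participant:
- mean of five ratings: v = (1 + 4rw)/5
- change from baseline: v + 1 − 2rb
- baseline-adjusted: v − rb²

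| | low | middle | high |
|---|---|---|---|
| rb / rw | 0.5 / 0.6 | 0.6 / 0.7 | 0.7 / 0.8 |
| v | 0.68 | 0.76 | 0.84 |
| change | 0.68 | 0.56 | 0.44 |
| adjusted | 0.43 | 0.40 | 0.35 |
| cut, 1 − adjusted/change | 37% | 29% | 20% |
| power at 0.8 SD, change | 76% | 83% | 91% |
| power at 0.8 SD, adjusted | 91% | 92% | 95% |
| same at alpha 0.025, change | 65% | 74% | 85% |
| same at alpha 0.025, adjusted | 84% | 87% | 91% |
| points detectable with 80% power, change | 5.1 | 4.6 | 4.1 |
| points detectable with 80% power, adjusted | 4.1 | 4.0 | 3.7 |

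Here 0.8 SD = 0.8 × 6 = 4.8 points, constant over the five times. Low column as an example: change SD = 6√0.68 = 4.95, noncentrality (4.8/4.95) × 2.828 = 2.74; adjusted SD = 6√0.43 = 3.93, noncentrality (4.8/3.93) × 2.828 = 3.45. The simulated powers also include the small cost of estimating the baseline slope.

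**3. The same comparison at the plan's effect.** The largest change-score SD is 4.95, so noncentrality is (10/4.95) × 2.828 = 5.71 and power is already close to 100%. Adjustment adds nothing material.

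**4. Group-by-time over five post-baseline ratings.** This test uses only the deviations of the five arm differences from their own mean. If all five are equal, every deviation is zero and the rejection rate equals alpha. Change scores give the same test, because subtracting one baseline shifts all five ratings of a participant equally. Simulated power at 10 points and SD 6 (low/middle/high correlations):

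| benefit pattern | group-by-time | group effect |
|---|---|---|
| constant 10 | 5/5/5% | at least 99% |
| 7 at 2 h, then 10 | 31/40/59% | at least 99% |
| 5 at 2 h, then 10 | 75/88/97% | at least 99% |
| fading: 10, 10, 10, 8, 6 | 53/67/86% | at least 99% |
| 10 at 2 h and 5 h only | about 100% | 60-79% (change), 52-60% (raw) |

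If correlations instead decay with time (AR(1), 0.5 to 0.9), the constant-benefit rate is 6.3-8.0% uncorrected and 4.5-4.7% with Greenhouse-Geisser correction. That is test size, not power. If 0hr were an extra level, group-by-time would have 99.9-100% power for a constant 10 points.

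**5. Choosing after the fact.** If the two tests are independent, 1 − 0.95² = 9.75%. Simulation with no drug effect gives 9.5-10.0%.

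**The case against.** The strongest reply is that the documents already point to the right test. B3.B bases power on a two-sample t-test of one difference between arms, and B3.A defines the outcome as change relative to placebo. The group effect is the nearest ANOVA counterpart. This stands as a lean. It is not a commitment: the power paragraph concerns a different test from the stated ANOVA, and the ANOVA sentence names no effect.

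A reader might infer that the primary analysis has only about 5% power. The documents do not support that. Nowhere do they say that group-by-time will decide, for PANSS or for the secondary outcomes. The figure also needs a benefit exactly equal at all five times. B1 gives the infusion as "for 4 hours) on positive and negative symptoms in symptomatic Early Course Schizophrenia (ECS"), so the 2 h rating falls during the infusion and exact constancy is a special case.

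A reader might also infer that baseline is ignored. It is not, if the change definition is followed; what is missing is a covariate. For that reason the comparison above is with change scores. The larger gains against raw scores (37/47/58% of variance) should not be claimed.

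It is fair to object that the gain rests on assumed correlations and an assumed 0.8 SD effect, and that this is a pilot of 32. Both are true. But B1 makes effectiveness the main purpose, the gain appears across the whole range tried, and adjustment needs no additional patients. PANSS timing, including 0hr, may be set out in the figure or schedule that the supplied text lacks.

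**Conclusion.** The point holds in a limited form. The primary PANSS analysis has no baseline covariate and leaves the deciding effect unstated.

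The material gain is from adjustment: a 20-37% smaller variance than change scores, and power at a constant 4.8 points rising from 76-91% to 91-95%. This rests on the assumed correlations, equal SDs of 6 and complete data. At the planned 10 points it makes no material difference, so the plan's power claim is not in doubt.

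The second part is about pre-specification. Group-by-time over post-baseline ratings answers a different question from whether the arms differ: 5% power for an exactly constant benefit and 31-97% for the sustained but uneven 10-point patterns. An open choice between the two effects roughly doubles the false-positive rate. The documents lean toward the arm difference, so this is a gap to close and not a demonstrated error. The change should be made before unblinding.

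**What to change.** Replace the PANSS sentence in B3.B with:

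> PANSS positive and negative scores at 2 h, 5 h, 1, 2 and 4 weeks will each be analysed with one likelihood-based repeated-measures model on all observed ratings (arm, visit, arm by visit, pre-infusion score by visit; unstructured covariance; Kenward-Roger degrees of freedom). The primary test is the baseline-adjusted arm difference averaged over the five times. Group-by-time and visit-specific differences are secondary.

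Also:
- State how alpha is handled over the two PANSS scores. Two tests at 0.05 give up to 9.75% (1 − 0.95²) if independent.
- State when the pre-infusion PANSS is rated. One should exist, because the outcome is a change and eligibility uses a PANSS total, but its timing is not in the text supplied.
- For cognition and retinal measures, state which effect is tested.

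Averaging over five times is a choice of target. If a same-day effect is what the trial seeks, name the adjusted mean of 2 h and 5 h as the primary contrast instead, before unblinding.

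Cost: SAP wording, standard R code and about one degree of freedom. The main downside is that the five-time average is weak for a same-day-only effect: 26/27/31% at 0.8 SD, against 83/87/92% for the 2 h/5 h contrast and 89% or more for group-by-time.
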